8.4.2. Analysis of Time-to-Event Secondary Efficacy Endpoints

Time-to-event secondary efficacy endpoints include:

- Time to CRR
- Time to PRR
- Time to UPCR < 0.5
- Time to death or renal-related events (see Section 3.2.1 for details regarding this endpoint)

For time-to-event endpoints, Kaplan-Meier methods will be used to estimate survival function, median survival time, and associated 95% CIs. The log-rank test (stratified for the randomization stratification factors) will be used to compare the two survival curves for each pairwise treatment comparison. Cox's proportional hazards model will be performed to assess differences between treatment groups. The model will include terms for treatment, stratification factors, and other select parameters including sex at birth, age, race, and baseline UPCR. Comparison of the survival distributions will use the score test for the hazard ratio from the Cox model. All statistical tests will be 2-sided.

Censoring rules

- Patients who are randomized but not treated will be censored at Week 1 (study day 1).
- Patients who die due to any cause prior to completing treatment at Week 53 will be censored at the day of the last non-missing UPCR assessment prior to death
- Patients who discontinue early from the study will be censored at the day of discontinuation

- Patients who are still on-study but have incomplete follow-up at the time of analysis will be censored at the last contact date
- Patients who have completed study treatment and did not experience the defined event through Week 53 will be censored at Week 53 + 1 day

Survival curves will be presented graphically for each pairwise treatment comparison. For each treatment group of interest, the number of patients at risk by time, number of patients who met the endpoint, number of patients who were censored, and median time to meet the endpoint along with the associated 95% CI will be presented for each treatment group of interest. The hazard ratio and associated 95% CI, p-value from the score test of the hazard ratio, and p-value from the log-rank test will also be presented on the graph.

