#### 10.6.2. Analysis of the Secondary Efficacy Endpoints

The secondary efficacy endpoint analyses will evaluate the proportion of patients treated with zetomipzomib compared with pooled placebo (in pairwise comparison) achieving the following:

- PRR at Week 37
- CRR at Week 53
- PRR at Week 53

- CRR at Week 25
- PRR at Week 25
- Percentage change from Baseline in UPCR by visit
- Time to CRR
- Time to PRR
- Time to death or renal-related events
- Proportion of patients achieving CRR (at Weeks 25, 37, and 53) with successful taper of prednisone or equivalent to ≤5 mg by Week 17
- Proportion of patients achieving CRR (at Weeks 25, 37, and 53) with no use of prednisone or equivalent during the 8 weeks prior to the renal response assessment
- Proportion of patients with UPCR ≤0.5 at Weeks 13, 25, 37, and 53
- Proportion of patients achieving CRR with UPCR ≤ upper limit of normal (ULN) at Weeks 25, 37, and 53
- Change from Baseline in clinical Systemic Lupus Erythematosus Disease Activity Index 2000 (SLEDAI-2K) score, excluding complement and anti-dsDNA components.
- Change from Baseline in EuroQol 5-Dimension 5-Level (EQ-5D-5L)

Time to death or renal-related events is defined as the first event occurring among the following:

- 1. Death
- 2. Doubling of serum creatinine
- 3. Proteinuric flare
- 4. Renal event-related treatment failure

The primary analysis of certain key secondary endpoints (ie, CRR at Week 53, PRR at Week 37 and Week 53) will follow the primary estimand principle, using the same approach as described in Section 10.6.1 and Table 6.

For a continuous endpoint such as percentage change from Baseline in UPCR by visit, data will either be observed or missing (ie, no NRI will be applied). The missing data will be handled by the following 2 approaches: (1) using MMRM model and (2) using MI to impute missing data and then applying MMRM model for analysis. The MMRM model (ie, Approach #1) will be the primary analysis method.

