3.2.1.7. Time to death or renal-related events

Time to death or renal-related events is defined as the first occurrence among the following:

- Death
- Doubling of serum creatinine from the baseline value
- Proteinuric flare
- Kidney failure (receiving dialysis or kidney transplantation)

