For statistical tests that are planned but not performed as a result of the multiplicity adjustment procedure (ie, other secondary endpoints), as well as for any other comparisons that are not subjected to multiplicity adjustment, nominal 2-sided p-values (without adjustment for multiplicity) will be provided as a measure of the strength of association between the endpoint and the treatment effect rather than formal tests of hypotheses.

Other (non-key) secondary and exploratory endpoints will be analyzed without controlling for the global family-wise type I error rate.

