8.5.3. Analysis of Binary Exploratory Endpoints

Binary exploratory endpoints include:

- Proportion of patients achieving PRR with successful taper of prednisone or equivalent to ≤5 mg by Week 17
- Proportion of patients achieving PRR with no use of prednisone or equivalent during the 8 weeks prior to the renal response assessment

- Proportion of patients who meet CRR by the China Center for Drug Evaluation (CDE) of NMPA Technical Requirements (Appendix 4), which is achieved if both of the following conditions are met:
 - urine protein quantification <0.5 g/24 h or urine protein/creatinine ratio (UPCR)
 <0.5 g/g;
 - eGFR reduction ≤10% of baseline or eGFR ≥90 mL/min/1.73 m².
- Proportion of patients who meet PRR by the CDE Technical Requirements definition (Appendix 4), which is achieved when both of the following conditions are met:
 - partial renal response can be regarded if urine protein quantification reduction ≥ 50% of baseline and <3.5 g/24 h, or UPCR reduction ≥ 50% of baseline and <3.0 g/g;

and

- eGFR reduction ≤ 10% of baseline or eGFR ≥90 mL/min/1.73 m².
- Proportion of patients who achieve urine protein quantification <0.5 g/24 h or urine protein/creatinine ratio (UPCR) <0.5 g/g and eGFR reduction ≤20% of baseline or eGFR >60 mL/min/1.73 m².
- Proportion of patients who achieve urine protein quantification <0.5 g/24 h or urine protein/creatinine ratio (UPCR) <0.5 g/g and eGFR reduction ≤15% of baseline or eGFR ≥60 mL/min/1.73 m².
- Proportion of patients who develop doubling of Baseline serum creatinine, kidney failure (receiving dialysis or kidney transplantation), or death
- Proportion of patients with Baseline SLEDAI-2K, excluding renal components, ≥6 with at least a 4-point improvement
- Proportion of patients with relapse or proteinuric flare
- Proportion of patients with SLE Flare Index of severe, moderate, or mild

The binary exploratory endpoints will be analyzed using similar CMH methods as the main analysis of the primary estimand.

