9.1.11. Death

The number and percentage of patients with at least one TEAE leading to death will be summarized by treatment group and overall. TEAEs leading to death will be further summarized by SOC and PT.

TEAEs leading to death will be presented in a separate listing, to include cause of death and death certificate availability information.

Any outcome of death without a corresponding fatal TEAE will be presented in a separate listing, to include cause of death and death certificate availability information.

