15. APPENDICES

APPENDIX 1. SCHEDULE OF ASSESSMENTS

Site Visit Week	Sc	1	2	5	9	13	17	21	25	29	33	37	41	45	49	53 EOT	56 EOS ^a	ETV
Assessment Window (days)	-35 to -1	NA	±2	±2	±2	±2	±2	±2	±2	±2	±2	±2	±2	±2	±2	±2	±2	NA
Informed consent	X																	
Medical history, including prior medications	X																	
Infectious disease blood tests ^b	X																	
Serum pregnancy test	X																	
Hepatitis B DNA ^c		X				X			X			X				X	X	X
Chest x-ray ^d	X																	
EULAR/ACR criteria for SLE	X																	
Physical examination ^e	X	X	X	X	X	X	X	X	X	X	X	X	X	X	X	X	X	X
12-lead ECG with QTcF interval ^f	X								X							X		X
Vital signs ^g	X	X	X	X	X	X	X	X	X	X	X	X	X	X	X	X	X	X
Clinical lupus disease assessmentsh	X	X				X			X			X				X	X	X
EQ-5D-5L		X				X			X			X				X	X	X
GTI assessment (including labs ⁱ)		X							X							X		X
Estimated GFR	X	X		X	X	X	X	X	X	X	X	X	X	X	X	X	X	X
Clinical laboratory tests ^j	X	X		X	X	X	X	X	X	X	X	X	X	X	X	X	X	X
Anti-dsDNA and complements (C3 and C4)	X	X		X	X	X	X	X	X	X	X	X	X	X	X	X	X	X
C1q autoantibody and quantitative IgM, IgG, IgA		X				X			X			X				X	X	X
Urine pregnancy test ^k		X		X	X	X	X	X	X	X	X	X	X	X	X	X	X	X
24-hour urine test	X					X			X			X				X	X	X
First morning void urine test	X			X	X	X	X	X	X	X	X	X	X	X	X	X	X	X
IV methylprednisolone ^l		X																
Background medications ¹	•																	\rightarrow

Site Visit Week	Sc	1	2	5	9	13	17	21	25	29	33	37	41	45	49	53 EOT	56 EOS ^a	ETV
Zetomipzomib or placebo administration ^m			← ze	tomipa	zomib	or plac	cebo a	dminis	tration	ı from	Week	1 to V	Veek 5	52 →				
Renal histopathology and immunohistopathology ⁿ	X															X		X
Urine biomarker measurements	X					X			X			X				X	X	X
Blood biomarker measurements ^o		X				X			X			X				X	X	X
Sparse PK assessment ^p									X			X						
Optional PK assessment ^p				X														
AEs and concomitant medications ^q	(AEs a	and con	ncomit	ant me	edicati	ons co	llected	l from	Week	1 to V	Veek 5	2, We	ek 53,	Week	56, and	etv →	

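### SAP 8.4.2 censors deaths before Week 53 in the analysis of time to death or renal-related events, although death is the first listed event of that endpoint

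*SAP*

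**What the plan says.** Definition. SAP 3.2.1.7 states: "Time to death or renal-related events is defined as the first occurrence among the following". The list that follows is death, doubling of serum creatinine, proteinuric flare and kidney failure. Protocol 2.2.1 has the same structure, as does Protocol 10.6.2: "Time to death or renal-related events is defined as the first event occurring among the following". In all three places death comes first.

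Analysis. SAP 8.4.2 names four endpoints: time to CRR, time to PRR, time to the UPCR threshold, and time to death or renal-related events. It prescribes Kaplan-Meier, log-rank and Cox methods for all four, then one common list of five censoring rules. The second rule is: "Patients who die due to any cause prior to completing treatment at Week 53 will be censored". The censoring day is that of the last non-missing UPCR before death. Only the fifth rule is limited to patients without an event; it covers treatment completers who "did not experience the defined event through Week 53 will be censored at Week 53 + 1 day".

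Status of the endpoint. SAP 8.1 places it outside the multiplicity procedure: "Other (non-key) secondary and exploratory endpoints will be analyzed without controlling for the global family-wise type I error rate".

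**The concern.** For time to CRR, PRR and the UPCR threshold, death is not an event, so censoring it agrees with the definitions. For the composite, the same rule takes the first listed event and codes it as a censored observation. The rule is triggered by the event itself, and nothing in 8.4.2 exempts this endpoint.

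Two things follow if it is programmed as written. First, the analysis no longer estimates the composite in its title. It estimates something closer to the risk of the renal components alone. Second, the censoring is informative for this endpoint: Kaplan-Meier treats a censored patient as still at risk, like those who remain, whereas this patient has just had one of the defined events. A difference in deaths between groups would not show in the result.

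**Working it through.** **1. The passages side by side**

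| Place | Role of death in this endpoint |
|---|---|
| Protocol 2.2.1 | First listed event |
| Protocol 10.6.2 | First listed event |
| SAP 3.2.1.7 | First listed event |
| SAP 8.4.2, second censoring rule | Censored at the last UPCR before death |

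**2. Does anything reconcile them?**

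- SAP 8.4.2 refers to Section 3.2.1 for this endpoint. That repeats the definition but does not switch off the censoring rule.
- The precedence clause in SAP Section 4 covers only that section's general guidance. It does not rank 3.2.1.7 against 8.4.2.
- SAP Section 13 lists changes from the protocol and has no entry on this.
- Protocol 10.6 gives the time-to-event methods but no censoring rules.

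**3. Effect of one death.** With 83 planned patients per group (SAP 4.2), a death with no earlier component event counts as 0 events where the definition requires 1. The crude event proportion in that group changes by 1/83 = 0.0120, or 1.2 percentage points.

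**4. Loss of follow-up time.** From SAP Appendix 1, ignoring the ±2-day visit windows:

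- If first-morning-void UPCR counts (row "First morning void urine test"), samples are 4 weeks apart from Week 5: up to about 4 × 7 = 28 days.
- If only 24-hour UPCR counts: up to 12 × 7 = 84 days between Weeks 13, 25 and 37, and up to 16 × 7 = 112 days between Weeks 37 and 53.
- Neither urine test is scheduled between Screening and Week 5. A death in the first four weeks could therefore be censored at a Screening sample, before study day 1.

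**5. Illustration of the whole effect.** The plan states no event rate, hazard ratio or power for this endpoint, so there is no figure to reproduce. The rates below are assumptions: Week 53 death risk d of 1% to 5% and non-fatal renal-event risk r of 10% or 20%. The simulation used 83 patients, independent exponential times, 1,000 runs per row, no other censoring, and UPCR on day 1 and every four weeks.

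| d | r | Week 53 incidence, death counted | Week 53 incidence, 8.4.2 rule | Mean events, death counted | Mean events, 8.4.2 rule |
|---|---|---|---|---|---|
| 1% | 10% | 10.9% | 10.0% | 9.05 | 8.22 |
| 2% | 10% | 11.8% | 10.0% | 9.80 | 8.19 |
| 3% | 10% | 12.8% | 10.1% | 10.66 | 8.25 |
| 5% | 10% | 14.6% | 10.0% | 12.11 | 8.09 |
| 1% | 20% | 20.9% | 20.1% | 17.36 | 16.63 |
| 2% | 20% | 21.5% | 20.0% | 17.88 | 16.47 |
| 3% | 20% | 22.5% | 20.1% | 18.65 | 16.40 |
| 5% | 20% | 24.2% | 20.3% | 20.13 | 16.36 |

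The death-counted column agrees with 1 − (1 − d)(1 − r); for d = 5% and r = 10% this is 1 − 0.95 × 0.90 = 14.5%. Under the 8.4.2 rule the estimate stays near r whatever the death risk. That is built into the rule, so the table shows its direction and is not a forecast. Between 0.7 and 4.0 events per group are lost.

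**The case against.** The best answer is that an event always takes precedence over censoring. Four of the five rules omit a no-event condition. Taken literally, the early-discontinuation rule would also censor a patient who reached CRR at Week 13 and left at Week 30, and nobody would program that. On the ordinary reading, death is already an event for the composite and the rule operates only for the three response endpoints. The endpoint's name, the pointer to Section 3.2.1 and the use of UPCR as the censoring date all support this.

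That reading is plausible and may be what the authors meant, but it does not remove the problem. The other rules concern something separate from the event. This one is triggered by the component event, so applying it gives the wrong coding, and two careful programmers could differ.

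Other objections stand in part:

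- Results change only if someone dies before completing treatment with no earlier component event.
- The death rates in the illustration are assumed and carry no weight for severity.
- Backdating before day 1 is possible but not certain, because a Week 1 urinalysis or an unscheduled sample might supply a UPCR.
- Deaths are not hidden. They are non-responses in the primary estimand (SAP 8.2.1). SAP 9.1.11 reports them by group: "TEAEs leading to death will be further summarized by SOC and PT". An exploratory binary endpoint in SAP 8.5.3 includes them: "Proportion of patients who develop doubling of Baseline serum creatinine, kidney failure (receiving dialysis or kidney transplantation), or death".

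**Conclusion.** The concern holds. SAP 8.4.2 as written conflicts with the definition in SAP 3.2.1.7 and Protocol 2.2.1 and 10.6.2, and nothing in either document resolves it. It should be fixed. The size is 1.2 percentage points of a group's crude event proportion per affected death, assuming the planned 83 per group, plus the lost follow-up time. The number of such deaths cannot be stated from the documents. The consequence is confined to one non-key secondary endpoint with nominal p-values; power, type I error, and the primary and key secondary results do not change.

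A separate mismatch does not bear on this conclusion. The fourth component of the composite is a treatment failure linked to a renal event in the protocol, but dialysis or transplantation in SAP 3.2.1.7, and SAP Section 13 does not record the change.

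**What to change.** In SAP 8.4.2:

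- State that for time to death or renal-related events, death from any cause is an event on the date of death.
- Limit the death-censoring rule to time to CRR, time to PRR and time to the UPCR threshold.
- Add to each censoring rule that it applies only to patients without a prior event.
- Say how a known death is handled for this endpoint when it follows study discontinuation, or occurs in a randomized patient who was never treated.

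Separately, use the same fourth component in Protocol 2.2.1 and 10.6.2 and SAP 3.2.1.7, or list the difference in SAP Section 13.

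The cost is a few sentences in the SAP, with no new data and no effect on patients. Making the change before unblinding avoids any suggestion that the rule was chosen after seeing the deaths.

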8.4.3. Analysis of Binary Secondary Efficacy Endpoints

Binary secondary efficacy endpoints include:

- Proportion of patients achieving CRR (at Weeks 25, 37, and 53) with successful taper of prednisone or equivalent to ≤5 mg by Week 17
- Proportion of patients achieving CRR (at Weeks 25, 37, and 53) with no use of prednisone or equivalent during the 8 weeks prior to the renal response assessment
- Proportion of patients with UPCR ≤0.5 at Weeks 13, 25, 37, and 53
- Proportion of patients achieving CRR with UPCR ≤ upper limit of normal (ULN) at Weeks 25, 37, and 53

Binary secondary efficacy endpoints will be analyzed using similar CMH methods as the main analysis of the primary estimand.

8.5. Exploratory Endpoints

All exploratory efficacy endpoints will be analyzed for the ITT Population (Class III/IV +/- V). A subset of exploratory endpoints will be analyzed for the pure Class V LN patients as described in Section 8.5.3.

8.5.1. Analysis of Continuous Exploratory Endpoints

Continuous exploratory endpoints include:

- Change from Baseline in antibodies (anti-dsDNA antibody, C1q autoantibody)
- Change from Baseline in complement (C3, C4)
- Change from Baseline in 24-hour urine protein
- Change from Baseline in serum albumin
- Change from Baseline in serum creatinine
- Change from Baseline in eGFR
- Change from Baseline in serum lipids (serum low-density lipoprotein [LDL] cholesterol, serum total cholesterol, serum triglycerides)

- Change from Baseline in blood hemoglobin A1c (HbA1c)
- Change from last visit in the GTI as measured by the GTI-CWS and the GTI-AIS
- Change from Baseline in SLEDAI-2K
- Change from Baseline in 28-joint counts (both tenderness and swelling counts)
- Change from Baseline in PGA score
- Change from Baseline in renal biopsy histopathology and immunohistopathology (optional; analysis of these endpoints is outside the scope of this SAP)
- Change from Baseline in IgM, IgG, and IgA

The continuous exploratory endpoints will be analyzed using similar MMRM methods as the main analysis of the continuous secondary efficacy endpoints. No MI analysis will be conducted for the continuous exploratory endpoints. Log-transformed values may be used for laboratory endpoints that are skewed and not normally distributed (eg, serum creatinine).

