#### 2.2.3. Exploratory Endpoints

The exploratory endpoints for patients treated with zetomipzomib compared with placebo include the following:

- Proportion of patients achieving PRR with successful taper of prednisone or equivalent to ≤5 mg by Week 17
- Proportion of patients achieving PRR with no use of prednisone or equivalent during the 8 weeks prior to the renal response assessment
- Proportion of patients who develop doubling of Baseline serum creatinine, kidney failure (receiving dialysis or kidney transplantation), or death
- Change from Baseline in antibodies (anti-dsDNA antibody, C1q autoantibody) and time to antibodies normalization or negative status (anti-dsDNA antibody normalization, anti-C1q antibody negative status)
- Change from Baseline in complement (C3, C4) and time to complement (C3, C4) normalization status
- Change from Baseline in 24-hour urine protein
- Change from Baseline in serum albumin
- Change from Baseline in serum creatinine
- Change from Baseline in eGFR

- Change from Baseline in serum lipids (serum low-density lipoprotein [LDL] cholesterol, serum total cholesterol, serum triglycerides)
- Change from Baseline in blood hemoglobin A1c (HbA1c)
- Change from baseline in the Glucocorticoid Toxicity Index (GTI) as measured by the Cumulative Worsening Score (GTI-CWS) and the Aggregate Improvement Score (GTI-AIS)
- Proportion of patients with Baseline SLEDAI-2K, excluding renal components, ≥6 with at least a 4-point improvement
- Change from Baseline in SLEDAI-2K
- Change from Baseline in 28-joint counts
- Change from Baseline in physician global assessment of disease activity (PGA) score
- Proportion of patients with relapse or proteinuric flare
- Time to relapse or proteinuric flare
- Proportion of patients with SLE Flare Index of severe, moderate, or mild
- Time to SLE Flare Index of severe, moderate, or mild
- Change from Baseline in renal biopsy histopathology and immunohistopathology (optional)
- Pharmacogenomics profile (ribonucleic acid [RNA] sequencing) and biomarkers, such as serum cytokine levels and circulating leukocytes to be determined in blood samples and urinary biomarkers
- Pharmacokinetics profile

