 To evaluate the speed of action of zetomipzomib compared with placebo To evaluate the clinical benefit of zetomipzomib compared with placebo To evaluate changes in serum levels of selected parameters in zetomipzomib compared with placebo To evaluate the efficacy of zetomipzomib compared with placebo on clinical lupus disease assessments To evaluate the efficacy of zetomipzomib compared with placebo on improving patient's quality of life To evaluate relapse in zetomipzomib compared with placebo To evaluate glucocorticoid-related AEs in zetomipzomib compared with placebo To evaluate renal histopathology and immunohistopathology (at selected sites based on feasibility) To evaluate the pharmacokinetics of zetomipzomib 	 Proportion of patients achieving PRR with successful taper of prednisone or equivalent to ≤5 mg by Week 17 Proportion of patients achieving PRR with no use of prednisone or equivalent during the 8 weeks prior to the renal response assessment Proportion of patients who develop doubling of Baseline serum creatinine, kidney failure (receiving dialysis or kidney transplantation), or death Change from Baseline in antibodies (anti-dsDNA antibody, C1q autoantibody) and time to antibodies normalization or negative status (anti-dsDNA antibody normalization, anti-C1q antibody negative status) Change from Baseline in complement (C3, C4) and time to complement (C3, C4) normalization status Change from Baseline in serum albumin Change from Baseline in serum albumin Change from Baseline in serum lipids (serum LDL cholesterol, serum total cholesterol, serum triglycerides) Change from Baseline in blood HbA1c Change from baseline in the GTI as measured by the GTI-CWS and the GTI-AIS Proportion of patients with Baseline SLEDAI-2K, excluding renal components, ≥6 with at least a 4-point improvement

Objectives Endpoints	
	Change from Baseline in SLEDAI-2K
	• Change from Baseline in 28-joint counts
	Change from Baseline in PGA score
	• Proportion of patients with relapse or proteinuric flare
	Time to relapse or proteinuric flare
	Proportion of patients with SLE Flare Index of severe, moderate, or mild
	Time to SLE Flare Index of severe, moderate, or mild
	• Time to antibodies normalization or negative status (anti-dsDNA antibody normalization, anti-C1q antibody negative status)
	• Time to complement (C3, C4) no longer being low
	• Change from Baseline in IgM, IgG, and IgA
	 Change from Baseline in renal biopsy histopathology and immunohistopathology (optional)*

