8.7. Glucocorticoid Toxicity Index

The following continuous GTI scores will be summarized by treatment group (mean, standard deviation, median, interquartile range, minimum, maximum) and post-baseline visit for the ITT Population:

• GTI-CWS

- Calculated as the sum of the maximum weighted scores for each of the 8 GTI domains from baseline through the visit of interest
- The GTI-CWS can only increase or stay the same for the duration of the study
- Lower GTI-CWS is associated with lower glucocorticoid toxicity over time

• GTI-AIS

- Calculated as the sum of the weighted scores for each of the 8 GTI domains at the visit of interest
- Lower GTI-AIS is associated with lower glucocorticoid toxicity over time

The 8 GTI domains will be listed for the ITT Population. Changes are with respect to the most recent previous on-study GTI assessment. Weighted scores for each category are noted in brackets below. More details can be found in the GTI Requirements Document (Appendix 5) and Weighting, Scoring and Analysis of the GTI (Appendix 6).

• Change in BMI

- Decrease of ≥5 BMI units [-36]
- Decrease of >2 to <5 BMI units [-21]
- No significant change (+/- 2 BMI units) [0]
- Increase of >2 to <5 BMI units [21]
- Increase of ≥5 BMI units [36]

• Glucose metabolism

- Improvement (decrease) in HbA1c AND decrease in use of glucose control medication [-44]
- Improvement (decrease) in HbA1c OR decrease in use of glucose control medication [-32]
- No significant change [0]
- Increase in HbA1c OR increase in use of glucose control medication [32]
- Increase in HbA1c AND increase in use of glucose control medication [44]

• Blood pressure (BP)

 Improvement (decrease) in BP AND decrease in use of BP control medication [-44]

- Improvement (decrease) in BP OR decrease in use of BP control medication [-19]
- No significant change [0]
- Increase in BP OR increase in use of BP control medication [19]
- Increase in BP AND increase in use of BP control medication [44]

• Hyperlipidemia

- Decrease in LDL AND decrease in use of lipid control medication [-30]
- Decrease in LDL OR decrease in use of lipid control medication [-10]
- No significant change [0]
- Increase in LDL OR increase in use of lipid control medication [10]
- Increase in LDL AND increase in use of lipid control medication [30]

• Steroid myopathy

- Moderate weakness to none [-63]
- Moderate to mild weakness [-54]
- Mild weakness to none [-9]
- No significant change [0]

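### SAP 8.5.1 and 8.7 score the exploratory Glucocorticoid Toxicity Index (GTI) against the previous assessment, while the protocol and SAP Table 1 define it as change from baseline and Section 13 records no change

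*SAP*

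**What the plan says.** Two places define the endpoint against baseline. Protocol 2.2.3 has "Change from baseline in the Glucocorticoid Toxicity Index (GTI) as measured by the Cumulative Worsening Score (GTI-CWS) and the Aggregate Improvement Score (GTI-AIS", and SAP 3.2 (Table 1) has "Change from baseline in the GTI as measured by the GTI-CWS and the GTI-AIS".

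Two places use a different reference. SAP 8.5.1, which governs the analysis, has "Change from last visit in the GTI as measured by the GTI-CWS and the GTI-AIS"; every other endpoint in that list is a change from baseline. SAP 8.7 states for the domain scores: "Changes are with respect to the most recent previous on-study GTI assessment".

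For the two summary scores, SAP 8.7 gives:
- AIS: "Calculated as the sum of the weighted scores for each of the 8 GTI domains at the visit of interest". Lower is better: "Lower GTI-AIS is associated with lower glucocorticoid toxicity over time".
- CWS: "Calculated as the sum of the maximum weighted scores for each of the 8 GTI domains from baseline through" the visit of interest, so it cannot fall.

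The schedule of assessments (Protocol Appendix 3, SAP Appendix 1) places GTI at Weeks 1, 25 and 53 and at early termination. SAP Section 13 lists departures as small as an added vital sign and added laboratory analytes, but not this one.

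**The concern.** The SAP contradicts both itself and the protocol on the reference point, and the conflict reaches the derivation. At Week 25 the previous assessment is Week 1, so the two definitions agree. At Week 53 the previous assessment is Week 25, so the rule in 8.7 yields a score that leaves out whatever happened between Weeks 1 and 25. A patient with no Week 25 GTI would be scored at Week 53 against Week 1, so a single visit column could mix two references.

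At stake is the stated exploratory objective on glucocorticoid-related adverse effects. Protocol 6.2.1.2 starts the oral steroid taper on Day 15 and aims for 5 mg/day or less by Week 17. The heaviest planned exposure therefore falls in the interval that the Week 53 AIS omits. A reader of Table 1 would take the reported Week 53 figure as change from baseline.

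**Working it through.** The plan gives no GTI figure to reproduce, so the check applies the SAP 8.7 weights to short patient courses.

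**Inputs (SAP 8.7)**
- BMI: 0 within 2 units; 21 in size for a change of more than 2 and less than 5 units; 36 for 5 or more. The sign follows the direction of change.
- Neuropsychiatric (NP): none/mild 11, mild/moderate 63, none/moderate 74; positive for worsening, negative for improvement. These add up: 11 + 63 = 74.
- Myopathy (9 + 54 = 63) and skin (8 + 18 = 26) are additive in the same way.

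**Formulas.** Let w(a→b) be the weight for the change from visit a to visit b.
- SAP 8.7 as written: Week 53 AIS = sum over domains of w(25→53).
- Protocol 2.2.3 and SAP Table 1: Week 53 AIS = sum over domains of w(1→53).
- In the three additive domains w(1→53) = w(1→25) + w(25→53), so the omitted term is exactly the Week 25 score.

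**Week 53 AIS, one domain at a time**

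| Course at Weeks 1, 25, 53 | Against Week 25 | Against Week 1 |
|---|---|---|
| BMI 0, +3, 0 | -21 | 0 |
| BMI 0, +1.9, +3.8 | 0 | +21 |
| BMI 0, +6, +6 | 0 | +36 |
| NP none, moderate, none | -74 | 0 |
| NP none, moderate, mild | -63 | +11 |
| NP none, moderate, moderate | 0 | +74 |
| NP moderate, none, none | 0 | -74 |

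**All courses.** Myopathy, skin and NP each have 3 × 3 × 3 = 27 possible courses over the three visits, with the same pattern in each domain:
- 4 courses give a negative (better) Week 53 AIS although the patient is no better than at baseline. In one of them (none, moderate, mild) the patient is still worse.
- 3 courses score sustained worsening as 0.
- 4 courses give a zero or positive score although the patient is better than at baseline. One is NP moderate, none, mild: +11 against -63.

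**CWS** (maximum over visits, with baseline itself scored 0)
- NP none, mild, moderate: max(0, 11, 63) = 63 as written; max(0, 11, 74) = 74 against baseline.
- BMI 0, +3, +6: max(0, 21, 21) = 21 as written; max(0, 21, 36) = 36 against baseline.

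**A further reading of 8.5.1.** If it means differencing scores that are already changes, BMI 0, +6, 0 gives AIS +36 at Week 25 and -36 at Week 53, a difference of -36 - 36 = -72. A CWS of 36 at both visits would give a difference of 0, which removes the toxicity accrued by Week 25.

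**The case against.** The strongest objection is that SAP 8.7 is only a summary. It points to Appendices 5 and 6 for the GTI requirements and scoring, and their content is not shown in the text available. If Appendix 6 accumulates visit-to-visit scores, the AIS would return to change from baseline for myopathy, skin and NP. This limits how firmly the Week 53 consequence can be stated. It does not remove the conflict between Table 1 and 8.5.1, and the visible text states no accumulation.

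A second objection is that early worsening is still reported. Scores are summarised at each post-baseline visit, so the patient with BMI 0, +3, 0 shows AIS +21 at Week 25 and keeps CWS 21 at Week 53. That is correct for abrupt early worsening. It does not help the slow course of BMI 0, +1.9, +3.8, where both scores stay at 0.

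A reader might go further and infer that the rule favours one arm, or systematically rewards patients who first get worse. The documents do not support this. The same rule withholds credit from early improvers who hold their gain, and early improvement is plausible because some patients enter at 40 mg/day of prednisone or more (Protocol 3.1). A reader might also assume that recovery from steroid toxicity comes mainly after Week 25. The taper schedule shows when exposure is heaviest; no section says when toxicity resolves.

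**Conclusion.** The inconsistency is established by the text, and the visible rule in 8.7 does not produce the endpoint that the protocol and Table 1 define. For individual patients the Week 53 AIS can differ by the full Week 25 score in the additive domains (up to 74 in NP) and can reverse sign. The CWS can differ as well.

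The importance is minor. The endpoint is exploratory and outside the type I error procedure. Only Week 53, or an early termination visit after Week 25, is affected. Infection is scored as an event and is untouched. The direction and size of any effect on the arm comparison cannot be determined from the documents.

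The conclusion on the Week 53 AIS assumes that the scoring appendices add no accumulation rule. The conflict over the reference point needs no such assumption.

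**What to change.** In SAP 8.5.1 and 8.7, score the seven change-based domains at Weeks 25 and 53 against the Week 1 baseline, and leave infection as an event score. Analyse the resulting AIS and CWS directly, with no further difference from the last visit.

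If Appendix 6 requires visit-to-visit scoring, keep the instrument score but label the Week 53 AIS as change from Week 25. Add the baseline-referenced score as the protocol endpoint, and record the departure in Section 13.

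Do not present the sum of the visit scores as change from baseline. That holds only for myopathy, skin and NP. For BMI, +1.9 then +1.9 sums to 0 against +21; +3 then +3 sums to 42 against 36; and +6 then -3 sums to 36 - 21 = 15 against 21.

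The cost is a few SAP sentences and one derivation. No new data are needed.
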